 - Those patients randomized to the self-removal group will be provided with a diagrammatic handout, illustrating proper removal of their catheter. They will be instructed to remove their indwelling urinary catheter at home on the morning of POD7. They will also be provided with the direct phone number of our Research Nurse and the pager number of our on-call staff, which they will use to contact the team if they are unable to void within 5 hours of catheter removal. If they are unable to void, the Research Nurse or on-call staff will arrange a clinic visit for the same day at one of three outpatient clinics (Clifton, West Chester, Kenwood) for replacement of an indwelling urinary catheter.
 - Those patients randomized to the office-removal group will schedule an office visit for POD6-8 at one of three outpatient clinics (Clifton, West Chester, Kenwood). At this visit the patient will undergo a backfill VT.
 - All patients will present to one of three outpatient clinics (Clifton, West Chester, Kenwood) at two weeks postoperative for a routine postoperative evaluation, measurement of PVR, urine dip, and completion of the patient questionnaire.
 - All patients will present to one of three outpatient clinics (Clifton, West Chester, Kenwood) at six weeks postoperative for a routine postoperative evaluation and urine dip.

- **Participants**
 - Study population: All women 18 years of age or older, who undergo vaginal vault suspension or robot-assisted laparoscopic sacrocolpopexy, with or without additional concomitant procedures by a physician at Cincinnati Urogynecology Associates, TriHealth for treatment of pelvic organ prolapse (POP) and who fail their VT prior to discharge will be approached for recruitment.
 - Inclusion/Exclusion criteria:

- Inclusion
 - Adults 18 years of age or older
 - Undergoing vaginal vault suspension or robot-assisted laparoscopic sacrocolpopexy by a physician at Cincinnati Urogynecology Associates, TriHealth for the treatment of POP
 - Concomitant procedures such as hysterectomy, suburethral sling, anterior or posterior colporrhaphy, bilateral salpingectomy or salpingoophorectomy
 - Failed voiding trial prior to discharge
- Exclusion
 - Unwillingness to participate in the study
 - Physical or mental impairment that would affect the subject's ability to self-remove indwelling urinary catheter, including patient's with Multiple Sclerosis, Dementia, Parkinsonism, or those who have impaired mobility or are wheelchair bound

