 - Bladder injury, fistula repair or other need for prolonged catheterization
- Sample size
 - A sample size was calculated to be 74 patients in each arm based on the following:
 - The estimated POUR requiring indwelling urinary catheter at 7 days postoperative is 16% (based on internal audit of data)
 - The non-inferiority margin was set at 15%. [11]
 - The power was set at 80%.
 - Due to estimated loss-to-follow-up rate of approximately 13%, the number of patient enrollment was set at 84 subjects in each group, 168 total.
- **Data Collection**
 - Primary outcome:
 - POUR at POD6-8 as defined by need for continued indwelling urinary catheter or intermittent self-catheterization.
 - Continued indwelling urinary catheter will be required in the following settings:
 - Self-removal group – inability to void or sense of incomplete bladder emptying after 5 hours of catheter removal
 - Office-removal group – voided volume less than two-thirds of the instilled volume or PVR greater than 100mL after backfill of up to 300mL

- Secondary outcomes
 - Scores on patient questionnaire collected at the two-week postoperative visit [12,13] (Patient Questionnaire and Visual Analog Scale)
 - Number of patient contact points (office visits, telephone calls and emergency room visits) regarding POUR or indwelling urinary catheter care up to 2 weeks postoperative.
 - PVR measurement at 2-week postoperative visit.
 - UTI diagnosed within 6 weeks postoperative (as defined by positive urine culture, or treatment with antibiotics by a provider).
 - Total duration (number of days) of urinary catheter use (including indwelling urinary catheter and intermittent self catheterization) within 6 weeks postoperative.
- General demographic data
 - Name, date of birth, age, race, weight, height, BMI, parity, tobacco use, medical comorbidities, date of surgery
- Data collection tool
- **Intervention or experimental aspect of the study**
 - Procedure
 - All patients of Cincinnati Urogynecology Associates who undergo vaginal vault suspension (VVS) or robot-assisted laparoscopic sacrocolpopexy (RSCP) will have a backfill VT on POD1 at 6am, per standard practice. The backfill VT will be performed by the nursing staff. Per protocol, up to 300ml sterile saline will be instilled into the bladder and the indwelling urinary catheter will be removed. Patients will be allotted 30 minutes to void. The instilled volume, voided volume, and PVR if needed will be recorded.

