 - Failure of backfill VT is defined by inability to void two-thirds of the instilled volume or PVR greater than 100mL.
 - Patients who fail the backfill VT postoperatively will have an indwelling urinary catheter reinserted and will be taught on its use by nursing staff. They will be approached for possible study enrollment by one of the study investigators.
 - If a patient agrees to participate in the study, she will receive a sealed envelope dictating to which group she will be randomized.
 - All subjects will be provided prescriptions for pain medication, bowel regimen, and cranberry supplements, per standard practice.

- Number of contact points (office visits, emergency room visits, and phone calls to care team) will be recorded during the first two weeks postoperative.
- Self-removal group
 - They will be provided with a diagrammatic handout, illustrating proper removal of their catheter (Diagram for Self-Removal)
 - They will be instructed to remove their indwelling urinary catheter at home on the morning of POD7 at approximately 7am.
 - They will be provided with the phone number of the Research Nurse and the pager number of the on-call staff.
 - On POD6 evening or POD7 morning, the Research Nurse will contact each patient to remind patients of the plan and review proper self-catheter removal.
 - On POD7 they will discontinue their indwelling urinary catheter by way of the instructions provided.
 - If they are UNABLE to void within 5 hours of catheter removal or have feelings of incomplete bladder emptying, they will call the Research Nurse or page the on-call staff. The Research Nurse or on-call staff will arrange a clinic visit for the same day at one of three outpatient clinics (Clifton, West Chester, Kenwood) for replacement of an indwelling urinary catheter.
 - A urine dip will be performed on the urine collected via the catheter. If positive for leukocyte esterase, white blood cells, or nitrites, the urine sample will be sent to the laboratory for culture
 - All urine culture results will be reviewed and if positive, will be treated and recorded. They will return to home with an indwelling urinary catheter and represent to the office for their two-week postoperative visit.
 - If they are ABLE to void within 5 hours of self-removal, they will remain without a catheter and present for their routine two-week postoperative visit the following week.
- Office-removal group

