nitrites, the urine dip will be sent to the laboratory for culture. All urine culture results will be reviewed and if positive, will be treated and recorded.

- Total duration of catheter use (indwelling urinary catheter or intermittent self-catheterization) will be extracted from the patients' chart and recorded at this time.

Statistical Analysis

- Descriptive statistics will be generated for demographic information such as age, race, BMI, Parity etc. The OR and 95% CI's of OR will be utilized to compare our primary outcome, the incidence of POUR between the two groups (self-removal and office-removal). Continuous variables such as the patient satisfaction questionnaire on VAS will be analyzed using independent samples t-tests or Mann-Whitney U test for significant difference between groups. Categorical variables will be tested using the Fisher's exact or Pearson Chi-square tests.

Ethical Considerations

- **Informed consent**
 - Patients who agree to participate in the study will sign a written informed consent. They will be consented by one of the stated investigators or trained Research Nurse and they will receive a copy of the signed informed consent statements (ICS). A copy will be put in their medical file.
- **Privacy information**
 - Extensive efforts will be made to ensure and maintain participant confidentiality. All identifying information will be maintained in a secure area at all times. Source documentation will be maintained in a separate folder. When documentation has to be made available for data analysis, copies of the source (Excel spreadsheets) with only Subject ID number visible and personal information obscured will be used. All communication between staff members regarding participant data will occur via the Subject ID number only. However, identifying information will be retained in the original/source documents.
 - The participant will be logged in the Excel spreadsheet and assigned a Subject ID number. Each participant will be assigned the next available Subject ID number. Once each Subject ID number has been assigned, it will not be reassigned. The Excel spreadsheet will be stored on a password

protected, encrypted TriHealth computer for ten years following study closure, and then purged.

Cost/Budget

Item	Amount	Qty	Total
Patient stipend for visit (mileage, time for travel, questionnaire completion, etc)	\$25.00	168	\$4,200.00

Estimated Period of time to complete study:

Estimated Period of Time to Complete Study	

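### The primary comparison is valid but unadjusted; pre-specifying adjustment for the POD1 voided fraction is a cheap efficiency gain of uncertain size

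*Combined protocol and SAP*

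**What the plan says.** The Statistical Analysis section states: "The OR and 95% CI's of OR will be utilized to compare our primary outcome, the incidence of POUR between the two groups". It names no covariate, regression model or stratification factor. Allocation is by sealed envelope, with no stratification on bladder function described. The variables named for descriptive statistics are demographic.

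The Procedure section says that all vaginal vault suspension and robotic sacrocolpopexy patients "will have a backfill VT on POD1 at 6am, per standard practice", and that "The instilled volume, voided volume, and PVR if needed will be recorded". Women who fail are then approached, and the envelope follows consent, so these volumes precede randomisation. Entry requires "Failed voiding trial prior to discharge", and the threshold is given as: "Failure of backfill VT is defined by inability to void two-thirds of the instilled volume or PVR greater than 100mL". The office-removal arm is judged on the same test at POD6-8. The self-removal arm is judged on inability to void, or a feeling of incomplete emptying, at 5 hours.

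**The concern.** The POD1 voided fraction (voided volume divided by instilled volume) is a pre-randomisation reading of the function that the primary outcome assesses about a week later. Enrolled women all failed on POD1, but the fraction can still vary among them. It can even exceed two-thirds in a woman who failed on PVR alone.

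Precision is scarce in this trial. At the planning rate, 148 evaluable women give about 148 × 0.16 = 24 events. If the baseline predicts the outcome, leaving it out makes the interval wider than it need be, and that interval decides non-inferiority. The stake is power and precision, not the validity of the test.

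**Working it through.** **Inputs from the Sample size section:** POUR rate 16% in both arms, margin 15% (read as an absolute difference, because that reading reproduces the sample size), power 80%, 74 per arm. No significance level is stated for the sample size. **Assumed, because the documents give no value:** the correlation r between POD1 voided fraction and POUR, with R² = r².

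**1. The plan's own figure.** n = 2p(1−p)(z₁₋α + z₀.₈₀)²/Δ².
- One-sided 0.05: 0.2688 × (1.645 + 0.842)²/0.0225 = 73.9, so 74. This matches the plan.
- One-sided 0.025 (a two-sided 95% interval): 0.2688 × (1.960 + 0.842)²/0.0225 = 93.8, so 94.

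The plan's 74 is reached with no adjustment, so the design does not depend on it.

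**2. Unadjusted precision.** SE = √(2 × 0.16 × 0.84/74) = 0.0603, or 6.03 points. Power = Φ(0.15/0.0603 − z₁₋α) = 80.1% at one-sided 0.05 and 70.2% at one-sided 0.025.

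**3. Effect of adjustment by formula.** The variance of the risk difference is multiplied by (1 − R²).

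| R² (r) | Power at 74, one-sided 0.05 | Power at 74, one-sided 0.025 | n per arm for 80%, one-sided 0.05 |
|---|---|---|---|
| 0 | 80.1% | 70.2% | 74 |
| 0.02 (0.14) | 80.8% | 71.0% | 73 |
| 0.05 (0.22) | 81.8% | 72.4% | 71 |
| 0.10 (0.32) | 83.6% | 74.6% | 67 |
| 0.15 (0.39) | 85.4% | 77.0% | 63 |

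**4. Effect by simulation** (74 per arm, 16% in both arms, logistic model standardised to a risk difference).
- Variance ratios, adjusted to unadjusted: about 0.99 at r = 0.11, 0.96 at 0.22, 0.90 at 0.32, and 0.81 to 0.85 at 0.40.
- Power with a 95% interval at r = 0.22, 0.32 and 0.40 (6,000 trials each): 72.0 to 73.3%, 70.3 to 74.2%, 71.8 to 77.8%.
- Power with a 90% interval: 81.5 to 82.1%, 79.9 to 82.8%, 81.8 to 85.8%.

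Each pair is unadjusted then adjusted on the same simulated trials, so compare within pairs; the Monte Carlo SE of one power figure is about √(0.72 × 0.28/6000) = 0.6 points.

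**5. Weak or unequal prediction** (12,000 trials, 95% interval).
- r = 0.10 in both arms: 72.2 to 72.0%. r = 0.15: 71.2 to 71.6%.
- r = 0.22 in the office arm and half that in the self-removal arm: 71.8 to 72.2%.
- r = 0.32 and 0.16: 70.9 to 73.1%. r = 0.32 and 0: a gain of 0.2 points.

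**6. Chance imbalance.** The SE of the difference in baseline means is √(2/74) = 0.164 SD. A one-SE imbalance shifts the risk difference by 0.164 × r × √(0.16 × 0.84) = 0.060r, which is 1.2, 1.8 and 2.4 points for r = 0.2, 0.3 and 0.4. Because √(2/74) × √(0.16 × 0.84) is the SE from step 2, this shift is the fraction r of an SE already in the interval. In 20,000 simulated trials per setting, with true rates of 31% and 16% (exactly at the margin) and odds ratios per SD from 1.0 to 2.72, the unadjusted test declared non-inferiority in 4.8% to 5.3% at nominal 5%. The adjusted test did so in 4.9% to 5.5%.

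**7. Cost if the covariate is useless.** At zero correlation, power moved from 80.7 to 80.1% (one-sided 0.05) and from 71.4 to 70.7% (one-sided 0.025).

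**The case against.** The strongest reply is that nothing here is wrong. Randomised arms may be compared without adjustment, the sample size assumed none, and steps 1 and 6 bear this out. That stands.

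A reader might infer that a chance difference in baseline voiding threatens the non-inferiority conclusion. At 16% in both arms, the largest observed difference that still meets the margin is 15 − 1.96 × 6.03 = 3.2 points (95% interval) or 15 − 1.645 × 6.03 = 5.1 points (90% interval), and a shift of 1.2 to 2.4 points looks large beside that. But that tolerance is computed from the same SE that already contains the shift, so setting the two side by side counts it twice. Adjusted and unadjusted conclusions differed in only about 2% to 7% of simulated trials with equal true rates.

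A reader might also infer that precision is certainly being lost. The documents do not support that either. They give no correlation and no spread of POD1 volumes. Correlations of 0.22, 0.32 and 0.40 correspond to odds ratios per SD of about 1.9, 2.7 and 3.9, which is moderate to very strong prediction. Enrolling only women who failed restricts the range, and the self-removal outcome is partly symptom-based, so prediction may be weak there. Step 5 shows how quickly the gain then fades.

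Finally, adding a covariate to a logistic model does not by itself sharpen the planned odds ratio: the adjusted odds ratio is conditional and has a larger standard error on the log scale. This is correct, and it is why the fix standardises to a risk difference. The mismatch between an odds-ratio analysis and a margin that works as a risk difference, and that between one-sided 0.05 and a 95% interval, matter more but are separate points.

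**Conclusion.** The point holds as a free or cheap improvement. The planned analysis is valid, but it does not use a baseline measure of the same function that is recorded before randomisation for every participant. Over an assumed correlation of 0 to 0.4, the variance of the risk difference falls by about 0% to 15-19%. Power changes from no gain (or a loss of up to about 1 point) to about 4 points with a 90% interval or 6 points with a 95% interval. The upper end needs strong and equal prediction in both arms. Confidence is high that the covariate is available and unused, and moderate at most on the size of the gain.

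**What to change.** Before outcomes are examined by arm, pre-specify the primary estimate as follows. Fit a logistic regression of POUR on arm and POD1 voided fraction (one linear term). Standardise it over all participants to a risk difference with a robust confidence interval, on the scale of the 15% margin. Report the unadjusted risk difference as a sensitivity analysis. Use the voided fraction and not POD1 PVR, which is recorded only when needed. Keep to this one term, given about 24 expected events.

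Add the two POD1 volumes to the study data set; the lists under Data Collection do not name them, although the data collection tool, which is not reproduced, may. State a simple rule for missing values, for example mean imputation pooled across arms.

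The cost is a short change of analysis wording, slightly more analysis and data extraction, and up to about 1 point of power if the covariate is not prognostic. No extra patients, visits or procedures are needed.
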